APPENDIX 3. SERIOUS ADVERSE EVENT REPORTING

SAEs, as defined in Section 16 Safety Assessments and Monitoring will be reported in accordance with ICH E2A Clinical Safety Data Management: Definitions and Standards for Expedited Reporting.

Site Responsibilities

All SAEs that occur during the course of the study must be reported to SCYNEXIS within 24 hours of the knowledge of the occurrence.

The Investigator will fill out the SAE form and provide as complete information as are available. At a minimum, subject number, the dates and times of the study drug administered, a narrative description of the event must be provided. An assessment by the Investigator as to the severity of the event and relatedness to study drug should also be provided, if possible. Investigator will report all SAEs to:

SCYNEXIS Inc.
[name]
[name]
[contact]
and

[contact] [contact] [contact]

The investigator will report SAE and any follow up information to the Research Ethics Board (REB) per REB procedures and requirements.

The investigator will provide SAE follow-up information as soon as information is available to SCYNEXIS.

SCYNEXIS Responsibilities

If the SAE is considered a Suspected, Unexpected Serious Adverse Reaction (SUSAR) SCYNEXIS or designee will create a CIOMS or a Medwatch 3500A Report for submission to the relevant regulatory authority within 15-days after SCYNEXIS has learned of the SAE. If the SUSAR is a fatal or life-threatening event, the reports will be sent within 7 days after SCYNEXIS has learned of the event.

Follow-up reports will be provided to regulatory agencies as soon as information is available according to the same reporting periods.

APPENDIX 4. PROTOCOL REVISION HISTORY

Revisions to Protocol dated 12 October 2021 (Protocol Version 2.0)

Current Version and Date: Protocol Amendment 2 (Protocol Version 3.0) dated 17 January 2022

Amended to delete the ~~strikethrough~~ text and include the **bolded** text

Protocol Section	Change and Rationale
Synopsis: Study Endpoints Synopsis: Statistical Analysis Section 9.1: Primary Endpoint Section 9.2: Secondary Endpoints Section 18.6.1.: Efficacy Assessments	
- Definition of “Clinical Cure” changed from a total composite score on the VSS Scale of “≤ 2” to “0”. In response to FDA comments- Addition of “Clinical Improvement” as another Clinical Outcome and Secondary Endpoint. Follow-on to above change 
Clinical Outcomes: Clinical Cure: partial or Complete resolution of signs and symptoms with total composite score of ≤ 2 on the VSS Scale and with no additional antifungal therapy required based on investigator's judgment. Clinical Improvement: partial resolution of signs and symptoms with total composite score of 1 or 2 on the VSS Scale and with no additional antifungal therapy required based on investigator's judgement.
 
Efficacy as measured by: The percentage of subjects with clinical improvement – Total composite score of 2 on the VSS Scale at the TOC and Follow-up (FU) visits. – Total composite score of 1 on the VSS Scale at the TOC and FU visits.

Synopsis: Study Visits Section 6: Schematic of Study Design Section 10.1.1: Study Visits Section 14: Study Procedures Section 15: Study Schedule	
Changes to Study Visits: In response to FDA comments
 
- TOC visit was changed from 14 days after EOT to 14 days after Baseline- FU Visit 14 (± 3) days after EOT was added- FU visit 30 (± 3) days after Baseline was added 
STUDY VISITS: The study will consist of a Screening visit on Day -2 (± 1), Baseline visit on Day 1 (if applicable, the Screening and Baseline visits can both be done on Day 1), Phone contacts on Days 3, 5 and 7 (± 1), a TOC visit 14 (± 3) days after EOT-Baseline and FU visits at: 14 days (± 3) days after End Of Treatment (EOT), 30 (± 4) after Baseline, 30 (± 4) days after EOT and 60 (± 4) days after EOT.
 
TOC visit (14 days [± 3] after EOT-Baseline): At this visit....
 
FU visit (14 days [± 3] after EOT): At this visit, treatment compliance will be reviewed and any AEs and/or concomitant medications evaluated. The investigators and the subjects will again rate the signs and symptoms of infection on the VSS Scale and the subjects will complete a QOL questionnaire. Vulvovaginal samples for fungal culture, species identification, and antifungal susceptibility testing will be obtained and sent to a designated central laboratory. Additional vaginal samples will be obtained for a KOH test and vaginal pH measurement by the local laboratory if symptoms persist or have worsened.
 
FU visits: 30 (± 4) days after Baseline, 30 (± 4) days after EOT and 60 (± 4) days after EOT: At the FU visits....


Synopsis Section 10.1. Overall Description of the Study Section 10.2 Blinding, Randomization and Stratification Section 14.13 Randomization
	
Study design changed from non-randomized without stratification, to randomized with stratification. In response to FDA comments
 
STUDY BLINDING, RANDOMIZATION, AND STRATIFICATION: This is an open-label study. There will be no blinding, randomization, or stratification. Subjects will be randomized to treatment, stratified by group based on the Candida species and presence or absence of underlying medical conditions.
 
Approximately 100 150 eligible subjects will be enrolled. Subjects will be randomized to receive oral ibrexafungerp 300 mg administered twice a day (BID) for either one, three, or seven consecutive days, stratified by group based on Candida species and presence or absence of underlying medical conditions.
												

Synopsis Section 18.1: Sample size Determination
	
Sample size increased from 100 to 150 subjects to be enrolled. Impact of response to FDA comments
 
Sample Size Determination:
 
The primary efficacy endpoint of the study is the percentage of subjects with clinical cure (partial or complete resolution of signs and symptoms with total composite score \leq of 0 on the VSS Scale with no additional antifungal therapy required based on investigator's judgment) at the TOC visit. As this is a single arm, a statement regarding CI will be produced. It is estimated that 100 eligible subjects will be enrolled.
 
This is an exploratory study, and no formal sample size calculation was performed. Approximately 150 subjects will be enrolled in allocation 50:50:50 in respect of 1, 3 or 7 days of treatment. Subjects will be randomized to treatment, stratified by group based on the Candida species and presence or absence of underlying medical conditions. A sample size of 150 subjects is estimated to be adequate to perform an initial assessment of efficacy.
												

Synopsis Section 10.3: Study Duration Section 12.1: Study Treatment Groups Section 12.4.: Ibrexafungerp Description Section 12.5.: Drug accountability Section 14: Study Procedures
	
 - Treatment Groups changed from 3 groups to 2 groups (Treatment Cycle 1). To simplify - Added potential for additional Treatment Cycle 2 treatment. To provide additional treatment option to patients with inadequate response - Study duration increased to potentially 130 days. As a result of the addition of Treatment Cycle 2 - IP will be provided in blister packs. Changed from bottles. Company logistics 
Ibrexafungerp Treatment Groups:
 
  
 Treatment Group	Criteria	*Ibrexafungerp Dose (300mg AM and 300mg PM) Randomization and Stratification	
   
 Group A	 
Subjects who do not fit criteria for Groups B and C
 
Subjects without underlying medical conditions AND known to have isolates other than C glabrata, C krusei, C auris
 	1 Day dosing N=50	
 
 Group B	 
Subjects with underlying medical conditions: DM, immunocompromised conditions (e.g. HIV), debilitation, immunosuppressive therapy (e.g. corticosteroids), recurrent VVC (≥ 3 episodes/year) AND/ OR known to have C glabrata, C krusei or C auris isolates
 	3 Day OR 7 Days dosing Randomized 1:1 N=50:50	
 
 Group C	Subjects known to have C glabrata, C krusei or C auris isolates	7 Day dosing	
  
	Treatment Group	Criteria	*Ibrexafungerp Dose (300mg AM and 300mg PM) Randomization and Stratification	Group A	
Subjects who do not fit criteria for Groups B and C
 
Subjects without underlying medical conditions AND known to have isolates other than C glabrata, C krusei, C auris
	1 Day dosing N=50	Group B	
Subjects with underlying medical conditions: DM, immunocompromised conditions (e.g. HIV), debilitation, immunosuppressive therapy (e.g. corticosteroids), recurrent VVC (≥ 3 episodes/year) AND/ OR known to have C glabrata, C krusei or C auris isolates
	3 Day OR 7 Days dosing Randomized 1:1 N=50:50	Group C	Subjects known to have C glabrata , C krusei or C auris isolates	7 Day dosing
Treatment Group	Criteria	*Ibrexafungerp Dose (300mg AM and 300mg PM) Randomization and Stratification											
Group A	
Subjects who do not fit criteria for Groups B and C
 
Subjects without underlying medical conditions AND known to have isolates other than C glabrata, C krusei, C auris
	1 Day dosing N=50											
Group B	
Subjects with underlying medical conditions: DM, immunocompromised conditions (e.g. HIV), debilitation, immunosuppressive therapy (e.g. corticosteroids), recurrent VVC (≥ 3 episodes/year) AND/ OR known to have C glabrata, C krusei or C auris isolates
	3 Day OR 7 Days dosing Randomized 1:1 N=50:50											
Group C	Subjects known to have C glabrata , C krusei or C auris isolates	7 Day dosing											

	
*Days of treatment is per CDC Guidelines (https://www.cdc.gov/std/treatment-guidelines/candidiasis.htm)
 
Enrollment will continue until the target number in each cohort is reached.
 
Treatment Cycle 2: A second treatment cycle will be allowed for subjects who did not achieve sufficient clinical improvement (e.g. VSS remains ≥ 3) on the randomized treatment (Cycle 1) as evaluated at the TOC visit or at the FU EOT+14 visits. A second treatment cycle will also be allowed for subjects with clinical cure/improvement/success who experience a recurrence before the last FU visit. During Cycle 2, subjects may receive additional treatment with ibrexafungerp for a period up to 14 days as recommended by the investigator and following discussion with the sponsor.
 
Study Duration: Each subject is expected to complete the study in approximately 65 days and up to approximately 130 days for subjects who require additional treatment and enter Treatment Cycle 2.
 
Oral tablets will be supplied in blister packs of four 150 mg tablets per blister. Each blister constitutes one day's dosing of 300 mg BID.

Section 16.3: Events of Clinical Interest	
Events of Clinical Interest – Removed. No longer required since Ibrexafungerp safety profile is well established
 
16.3. Events of Clinical Interest - Not Applicable
 
The following are considered events of clinical interest (ECIs) if they occur after dosing, and must be reported by the site when it becomes aware of the ECI:
 
• ALT or AST $> 8 \times$ the upper limit of normal (ULN), confirmed by repeat testing• ALT or AST $> 5 \times$ ULN for more than 2 weeks if new compared to Baseline, confirmed by repeat testing• ALT or AST $> 3 \times$ ULN and total bilirubin $> 2 \times$ ULN if new compared to Baseline, confirmed by repeat testing• ALT or AST $> 3 \times$ ULN, confirmed by repeat test, with the appearance of fatigue, nausea, vomiting, right upper quadrant pain or tenderness, fever, rash, and/or eosinophilia ($> 5\%$)

Revisions to Protocol dated 03 September 2021 (Protocol Version 1.0) Current Version and Date: Protocol Amendment 1 (Protocol Version 2.0) dated 12 October 2021.	
Protocol Section	Change and Rationale
Section 4. Revision History	This section is added to track revisions to the protocol. Numbering of sections changed throughout.
Section 6 Protocol Synopsis Section 7 Schematic of Study Design Section 9 Study Objectives Section 10 Study Endpoints Section 11.1 Study Visits Section 11.2 Study Assessments Section 15.12 Quality of Life Questionnaire Section 19.6.1 Efficacy Analysis	Add text that the Quality of Life Questionnaire will be completed at Baseline, TOC and Follow-up visits to sections where it was previously omitted.
Section 12.2 Inclusion Criteria	Add text to clarify the pregnancy prevention requirements as part of Inclusion Criteria “Subject is not pregnant or lactating and plans not to become pregnant. Women of childbearing potential < 1 year post-menopausal must agree to and comply with using one barrier method (male condom, female condom, and diaphragm) plus one other highly effective method of birth control, or sexual abstinence, from the time of consent through 10 days after the completion of study therapy.”

| Abbreviation | Definition |
|--------------|------------------------------|
| AE | Adverse event |
| ATC | Anatomical Therapeutic Class |

| Abbreviation | Definition |
|--------------|--|
| BID | Twice a Day |
| BMI | Body Mass Index |
| CRF | Case report form |
| EOT | End of therapy |
| FU | Follow Up |
| HIV | Human immunodeficiency virus |
| ITT | Intent-to-Treat |
| MedDRA | Medical Dictionary for Regulatory Activities |
| MITT | Modified Intent-to-Treat |
| PP | Per-Protocol |
| PT | Preferred term |
| QOL | Quality of Life |
| SAP | Statistical analysis plan |
| SAE | Serious adverse event |
| SD | Standard deviation |
| SOC | System organ class |
| TEAE | Treatment-emergent adverse event |
| TFLs | Tables, figures, and listings |
| TOC | Test of Cure |
| VVC | Complicated Vulvovaginal Candidiasis |
| VSS | Vulvovaginal Signs and Symptoms Scale |
| WHODrug | World Health Organization Drug Enhanced Dictionary |

3. Introduction

The purpose of this statistical analysis plan (SAP) is to describe the procedures and statistical methodologies that will be used in the analysis and reporting of results for SCYNEXIS, Inc. Protocol SCY-078-307b.

This document is prepared based on the following documents:

- the study protocol version 3.0 dated 17 January 2022.
- the case report form (CRF) version 1.2 dated 9 September 2022.

Readers are referred to the final study protocol, the CRF, and CRF completion guidelines for details of the study design, conduct and data collection. This SAP must be finalized prior to the locking of the clinical database for this study. The mock tables, figures, and patient data listings (TFLs) are provided in a separate document.

4. Objectives and Endpoints

4.1. Objectives

4.1.1. Primary Objectives

- To evaluate the efficacy of oral ibrexafungerp in subjects with complicated VVC who failed fluconazole therapy, based on clinical cure.

4.1.2. Secondary Objectives

- To evaluate the efficacy of oral ibrexafungerp in subjects with complicated VVC who failed fluconazole therapy, based on mycological and clinical outcomes.
- To evaluate the safety and tolerability of oral ibrexafungerp in subjects with complicated VVC who failed fluconazole therapy.

4.1.3. Exploratory Objectives

- To evaluate the efficacy of oral ibrexafungerp in subjects with complicated VVC who failed fluconazole therapy, based on QOL outcomes.

4.2. Endpoints

4.2.1. Primary Endpoints

- Efficacy as measured by the percentage of subjects with clinical cure (total composite score of 0 on the VSS Scale (refer to [Appendix 1](#)) with no additional antifungal therapy required based on investigator's judgment) at the TOC visit.

4.2.2. Secondary Endpoints

Efficacy as measured by:

- The percentage of subjects with clinical improvement:
 - Total composite score of 2 on the VSS scale at the TOC and FU visits
 - Total composite score of 1 on the VSS scale at the TOC and FU visits.
- The percentage of subjects with total composite score equal or less than 2 and equal or less than 1 on the VSS scale at the TOC and FU visits.
- The percentage of subjects with clinical success (at least 50% reduction from baseline in the total composite VSS score) with no additional antifungal therapy required based on investigator's judgment) at the TOC and FU visits.
- The percentage of subjects with mycological response (defined as a negative culture for growth of *Candida spp.* or subject is asymptomatic, therefore culture not done) at the TOC and FU visits.
- The percentage of subjects with both clinical cure and mycological response at the TOC and FU visits.
- The percentage of subjects with clinical cure at the FU visits.
- The absolute change in total composite VSS score from baseline to the TOC and FU visits.

Exploratory Endpoints:

- Absolute improvement in QOL outcomes at TOC and FU visits compared to baseline as measured by QOL survey.
- Subjects whose signs and symptoms have resolved enough that additional antifungal treatment was not required based on clinical judgement.
- Time to resolution of symptoms.

Safety and Tolerability as measured by:

Adverse events (AEs), vital signs, treatment discontinuation, and safety laboratory tests.

5. Study Design

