9.2. Secondary Endpoints

Efficacy as measured by:

- The percentage of subjects with clinical improvement:
 - Total composite score of 2 on the VSS scale at the TOC and FU visits
 - Total composite score of 1 on the VSS scale at the TOC and FU visits
- The percentage of subjects with clinical success (at least 50% reduction from baseline in the total composite VSS score) with no additional antifungal therapy required based on investigator's judgment) at the TOC and FU visits.
- The percentage of subjects with mycological response (defined as a negative culture for growth of *Candida* spp. or subject is asymptomatic, therefore culture not done) at the TOC and FU visits.
- The percentage of subjects with both clinical cure and mycological response at the TOC and FU visits.
- The percentage of subjects with clinical cure at the FU visits.
- The absolute change in total composite VSS score from baseline to the TOC and FU visits.

Exploratory Endpoints:

- Absolute improvement in QOL outcomes at TOC and FU visits compared to baseline as measured by QOL survey.
- Subjects whose signs and symptoms have resolved enough that additional antifungal treatment was not required based on clinical judgement.
- Time to resolution of symptoms.

Safety and tolerability as measured by:

Adverse events (AEs), vital signs, treatment discontinuation, and safety laboratory tests.

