10.1.1.4. TOC visit (14 \pm 3 days after Baseline)

At this visit, study drug container(s) will be returned, reviewed, and treatment compliance evaluated. The investigators and the subjects will again rate the signs and symptoms of infection on the VSS Scale and the subjects will complete a QOL questionnaire.

Vulvovaginal samples for fungal culture, species identification, and antifungal susceptibility testing will be obtained and sent to a designated central laboratory. Additional vaginal samples will be obtained for a KOH test and pH measurements by the local laboratory if symptoms persist or have worsened. AEs and/or concomitant medications will be evaluated.

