14.10. Vulvovaginal Samples for KOH and Fungal Culture

At Screening, a vulvovaginal specimen will be obtained for direct microscopic examination with 10% KOH. Subjects must have a positive KOH test at screening to be enrolled. The screening KOH will be assessed at the site by the investigator or qualified designee. A vaginal sample will also be obtained at screening, at the TOC and at the first FU visit at 14 days after EOT for fungal culture and species identification by the central laboratory and for susceptibility testing against ibrexafungerp and additional antifungal agents (per CLSI M27-A3 guidelines). If there is persistence or recurrence of vulvovaginal symptoms, additional vulvovaginal specimens will be collected for KOH testing at the TOC and at the FU visits, and for fungal culture at the FU visits. Samples will also be obtained at any unscheduled visit, if needed.

If the subject experiences persistence or worsening or recurrence of symptoms that per the investigator's assessment (e.g. symptoms ≥ 4) warrant the use of rescue antifungal therapy, the subject may be enrolled into Treatment Cycle 2 and receive additional treatment with ibrexafungerp for a period up to 14 days as recommended by the investigator and following discussion with the sponsor.

Whether or not a subject enters Treatment Cycle 2, or be prescribed rescue therapy, a vaginal examination with collection of samples for KOH (assess at the site) and culture should be completed prior to initiation of Treatment Cycle 2 or rescue therapy. If the KOH test is negative, the investigator should consider other causes for the persistence or worsening of the symptoms and antifungal rescue medication may not be indicated. If the collection of the vaginal culture is not possible prior to the initiation of the rescue therapy, it should still be collected as soon as possible after rescue therapy is given.

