15. STUDY SCHEDULE

Detailed schedules of all study visits and procedures are presented in Schedule of Visits and Procedures ([Table 1](#)).

The actual visits will be dependent on the Dosing Group i.e there may be overlapping visits.

Subjects entering Treatment Cycle 2, will follow the same Schedule of Visits and Procedures, starting with Baseline visit and may have visits that are Not Applicable during Treatment Cycle 1.

Table 1: Schedule of Visits and Procedures (Study SCY-078-307b)

Visit	V1 Screening ^a	V2 Baseline ^a	At Home	V3 TOC	V4 FU	V5 FU	V6 FU	V7 FU	Unscheduled Visits ^b
Day (allowable window)	Day -2(±1)	Day 1	Days 2-7	14 ±3 days post Baseline	14 ±3 days post EOT	30±4 days post Baseline	30 ±4 days post EOT	60 ±4 days post EOT	
Study Procedures									
Informed consent	X								
Enrollment and assignment of Subject ID number	X								
Inclusion/exclusion criteria ^c	X	X							
Medical history and demographics	X								
Abbreviated physical exam	X			X					If needed
Vital Signs ^k	X	X		X					If needed
Urine pregnancy test ^c	X			X					If needed
Safety laboratory blood tests ^d	X			X					If needed

Visit	V1 Screening ^a	V2 Baseline ^a	At Home	V3 TOC	V4 FU	V5 FU	V6 FU	V7 FU	Unscheduled Visits ^b
Day (allowable window)	Day -2(±1)	Day 1	Days 2-7	14 ±3 days post Baseline	14 ±3 days post EOT	30±4 days post Baseline	30 ±4 days post EOT	60 ±4 days post EOT	
Rating of vulvovaginal symptoms by the Subject^e	X	X	X	X	X	X	X	X	If needed
Vaginal Examination and rating of vulvovaginal signs by the Investigator^e	X			X	X	If symptoms	If symptoms	If symptoms	If needed
Vulvovaginal sample for other pathogens^e	X			If needed	If needed	if needed	If needed	If needed	If needed
Vulvovaginal sample for KOH and pH^e	X			If symptoms	If symptoms	If symptoms	If symptoms	If symptoms	If needed
Vulvovaginal sample for fungal culture^e	X			X	X	If symptoms	If symptoms	If Symptoms	If needed
Quality of Life Questionnaire		X		X	X	X	X	X	
Study drug dosing		X	X						
Study drug container(s) collection and subject data reviewed				X					
Phone Contact^h			X						
Prior and concomitant medication reviewⁱ	X	X	X	X	X	X	X	X	X
AE monitoring^j	X-----X				X	X	X	X	X

Abbreviations: AE = adverse event; D = day; TOC = test of cure; V = visit; FU = follow up

- a) Screening and Baseline may occur on the same day.
- b) Unscheduled visits can occur if the investigator determines there is a need for one outside of the scheduled per protocol visits.

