18.4. Handling of Missing Data, Dose Adjustments, and Early Withdrawals

For the efficacy analyses, subjects who do not have a TOC assessment will be assigned as treatment failures. For subjects who withdraw from the study early, every effort will be made to collect TOC visit information at the point of withdrawal.

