6.4.2. Secondary Efficacy Analyses

6.4.2.1. Definition of Secondary Endpoint

The following treatment outcome definitions will be used for the assessment of efficacy relative to baseline: Clinical Outcome.

- Clinical Cure: Complete resolution of signs and symptoms with total composite score of 0 on the VSS Scale and with no additional antifungal therapy required based on investigator's judgment.
- Clinical Improvement: Partial resolution of signs and symptoms with total composite score of 1 or 2 on the VSS Scale and with no additional antifungal therapy required based on investigator's judgement.
- Clinical Success: At least 50% reduction from Baseline in the total composite VSS score with no additional antifungal therapy required based on investigator's judgment .
- Clinical Failure: Persistence and/or worsening of signs and symptoms or need for additional antifungal therapy (this definition also applies to cycle 2 patients).

The following mycological outcome definitions will be used for the assessment of subjects with mycological response.

- Mycological Eradication: Negative culture for growth of *Candida* species .
- Presumed Eradication: Subject is asymptomatic, therefore cultures not done .
- Mycological Persistence: Positive culture for growth of *Candida* species.

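### The mycological response definition lets an asymptomatic subject with no culture count as a responder at TOC and EOT+14, where the protocol requires a culture from everyone

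*SAP*

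**What the plan says.** **Endpoint.** Protocol 9.2 defines "The percentage of subjects with mycological response (defined as a negative culture for growth of *Candida* spp. or subject is asymptomatic, therefore culture not done", and SAP 4.2.2 repeats it: "subject is asymptomatic, therefore culture not done) at the TOC and FU visits". Both apply it to TOC and to all follow-up visits. The outcome category behind the second route, in SAP 6.4.2.1 and Protocol 18.6.1.2, also has no visit limit: "Presumed Eradication: Subject is asymptomatic, therefore cultures not done". A further secondary endpoint combines clinical cure with mycological response at the same visits.

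**Culture schedule.** For TOC, Protocol 10.1.1.4 states: "Vulvovaginal samples for fungal culture, species identification, and antifungal susceptibility testing will be obtained and sent to a designated central laboratory". Section 10.1.1.5 says the same for the EOT+14 visit. Section 14.10 confirms both: "A vaginal sample will also be obtained at screening, at the TOC and at the first FU visit at 14 days after EOT". In Table 1 the row "Vulvovaginal sample for fungal culture" has a plain X at Screening, V3 (TOC) and V4 (EOT+14), and is conditional on symptoms at V5, V6 and V7.

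**Missing data.** SAP 6.1.2 imputes nothing unless another rule says so. It has no rule for a culture missed at an attended visit. Protocol 18.4 says that, for efficacy, "subjects who do not have a TOC assessment will be assigned as treatment failures".

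**The concern.** Presumed eradication makes sense where the protocol itself omits the culture because the subject has no symptoms. That is the case only at V5 to V7. At TOC and EOT+14, absence of symptoms is never a protocol reason to omit the sample. There the clause can only reach a subject whose required culture was not obtained, and it offers her a route to success.

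These are the only scheduled post-treatment visits with mycology in everyone. For one-day dosing they nearly coincide, since treatment ends on Day 1. The composite inherits the problem: a clinically cured subject has VSS 0 and is asymptomatic on any definition, so a missed culture lets her meet both parts without mycological evidence. Any resulting error is one-sided, upward. Protocol 7.1.1 itself notes that *Candida* can persist in the vagina after azole treatment, so freedom from symptoms is not the same as a negative culture.

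**Working it through.** The plan states no expected mycological response rate or missed-culture rate, so there is no figure to reproduce.

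**Step 1: definition against schedule**

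| Visit | Culture required from | Can lack of symptoms explain a missing culture? |
|---|---|---|
| V3, TOC | everyone | no |
| V4, EOT+14 | everyone | no |
| V5 to V7 | symptomatic subjects | yes |

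The clause fits the schedule only in the last row.

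**Step 2: size.** All three inputs are assumptions:
- a = share asymptomatic at the visit, 50 to 70%
- m = share of those without a culture, 5 to 20%
- r = share of those missed cultures that would have been negative, 60 to 80%

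Against complete culture data:
- the clause overstates the rate by a × m × (1 − r);
- counting the same subjects as non-responders understates it by a × m × r;
- moving from one rule to the other lowers the rate by the sum, a × m.

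| a, m, r | Clause overstates | Non-response understates | Difference |
|---|---|---|---|
| 50%, 5%, 80% | 0.5 × 0.05 × 0.2 = 0.5 points | 0.5 × 0.05 × 0.8 = 2.0 | 2.5 |
| 70%, 10%, 60% | 0.7 × 0.10 × 0.4 = 2.8 | 0.7 × 0.10 × 0.6 = 4.2 | 7.0 |
| 70%, 20%, 60% | 0.7 × 0.20 × 0.4 = 5.6 | 0.7 × 0.20 × 0.6 = 8.4 | 14.0 |

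The first and third rows are the extremes for the overstatement and for the difference. The understatement ranges somewhat wider over all combinations, from 0.5 × 0.05 × 0.6 = 1.5 to 0.7 × 0.20 × 0.8 = 11.2 points.

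**Step 3: cross-check.** As a proxy for a, take the clinical cure rates in the two earlier Phase 3 studies (Protocol 7.1.4), 50.5% and 63.3%. With m from 5 to 20% and an assumed 10 to 50% of missed cultures positive, the overstatement runs from 0.505 × 0.05 × 0.10 = 0.3 points to 0.633 × 0.20 × 0.50 = 6.3 points. Those studies excluded patients with treatment failure, so the proxy is loose.

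**Step 4: in subjects.** With 50 per regimen, one subject moves the rate by 1/50 = 2 points, and by more if the MITT set is smaller. The product a × m × 50 runs from 1.25 to 7 subjects whose classification depends on the rule.

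**Step 5: the rate among cultured subjects.** This is not free of bias either, because it drops asymptomatic subjects, who are more likely to be negative. Assume further that 70% of symptomatic subjects are culture-positive and none lacks a culture. With a = 63.3%, m = 10% and 30% of asymptomatic subjects positive, the complete-data rate is 55.3%, the clause gives 57.2%, the cultured-only rate is 54.3%, and missing as non-response gives 50.9%.

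**The case against.** **The wording may not reach a missed culture.** The clause says the culture was not done because the subject had no symptoms. A sample skipped by error was not omitted for that reason, and one taken and then lost was, in a sense, done. With the no-imputation rule, such subjects could simply stay missing. This stands as a possible reading, so the documents cannot be said to score missing as success outright. But the definition names TOC explicitly, and nothing tells the programmer how to separate the two cases.

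**Protocol 18.4 does not settle it.** A reader might infer that the clause contradicts the failure rule. That rule covers subjects with no TOC assessment. It does not say whether one absent specimen at an attended visit qualifies, and it is silent on EOT+14.

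**Missing as non-response can be worse.** This stands. Whenever more than half of the missed cultures would have been negative, it lies further from the truth than the present clause, as Step 2 shows.

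**The EOT+14 culture might be conditional.** Table 1 footnote f limits follow-up examinations to symptomatic subjects without exempting EOT+14. It concerns examinations, however. The culture row and Sections 10.1.1.5 and 14.10 are unconditional.

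**Reach is limited.** This stands. It is a secondary endpoint in an exploratory study, summarised by counts and percentages without a test. Nothing in the documents shows that cultures will be missed. Eradication and presumed eradication are separate categories, and the table shells are in another document, so it cannot be said that presumed cases would go unreported.

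**Conclusion.** The mismatch between definition and schedule is real and should be resolved before database lock. At TOC and EOT+14, an asymptomatic subject without the required culture can be counted as a responder, and as meeting the composite if she is clinically cured. No rule clearly prevents it. Under the stated assumptions the overstatement is 0.5 to 5.6 points. It is zero if no such culture is missed, if every missed one would have been negative, or if the analyst leaves those subjects missing. The primary endpoint is unaffected.

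Two stronger inferences are not supported. One is that a subject with rated signs but no symptoms and no culture is certainly a responder: neither document says whether asymptomatic means a symptom score of 0 or a total VSS of 0. The other is that the endpoint wording tells sites to skip the culture: the visit instructions order it plainly.

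**What to change.** In SAP 4.2.2 and 6.4.2.1, and in Protocol 9.2 and 18.6.1.2 if amended:

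- Limit presumed eradication to V5 to V7.
- Base response at TOC and EOT+14, and the mycological part of the composite, on an actual culture result. Do not count a missing culture at an attended visit as a response.
- Report the rate among subjects with a culture, and the number of missing cultures by visit and regimen.
- Show two bounds: all missing cultures as non-response, and the current rule.
- State whether asymptomatic means symptom score 0 or total VSS 0, and say how a symptomatic subject without a culture is classified, since she now fits no category.

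The cost is a few sentences and one more table, with no new data. The reported rate may be lower or less precise. Counting all missing as non-response would lower it by 2.5 to 14 points under the same assumptions. In the scenarios tabulated above that rule understates the rate by 2.0 to 8.4 points, so it belongs in the report as a bound and not as the only rule.
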